9. STUDY POPULATION

The study population will be described by the parameters below. Listings and summaries will include all randomized subjects unless otherwise noted.

9.1 Subject Disposition

Frequencies and percentages of subjects who discontinued the study treatment and/or study will be summarized. Reasons for discontinuation will also be summarized. The listing of subject disposition will include dates and times (if applicable) of randomization, dosing, and EOS; and reasons for study treatment and/or study discontinuation (if applicable).

9.2 Informed Consent and Eligibility

Informed consent (for the Screened Population) and eligibility parameters will be listed. Reasons for screen failure will be summarized.

9.3 Visit Summaries and 10-Day Diary

Listings of visit summaries and 10-day diary entries will be provided.

Confidential Page 16 of 35

9.4 Protocol Deviations

A listing of protocol deviations will include protocol version and the category of the deviation (to be determined). Frequency and percentage of subjects in each deviation category will be summarized.

9.5 Analysis Populations

The analysis populations defined in Section 7 will be described in terms of the identification of subjects in each population and the frequency distribution of each population. The number of randomized subjects will also be described. Number of screened subjects will be the denominator for percentage of subjects randomized, and the number randomized will be the denominator for percentage of subjects in the Safety, mITT, and PP populations.

A listing of analysis populations will be produced showing the analysis population(s) to which each subject belonged.

9.6 Demographic and Baseline Characteristics

Demographic and other baseline characteristics will be summarized both overall and by treatment group. Parameters will include sex; age at informed consent; age stratum for randomization; race; ethnicity; weight, height, and body mass index (BMI) at screening; baseline otitis media risk factors (private or public health insurance, mother's education level, attends daycare, at least 3 other children in household, smoker in household), study site, and tympanogram status (yes or no).

9.7 Medical History

Reported medical conditions will be coded using the Medical Dictionary for Regulatory Activities (MedDRA), version 21.0, to a System Organ Class (SOC) and Preferred Term (PT). Medical history will be summarized by SOC and PT.

10. TREATMENTS

Treatments include study treatment, oral antibiotic treatment, device incidents, device experience, prior medications, and concomitant medications.

10.1 Study Treatment Exposure

Exposure to study treatment will be expressed as total exposure, mean daily exposure, and duration of exposure.

Exposure per study treatment administration E_a (mg) will be calculated as

$$E_a(mg) = (S_{L_a} + S_{R_a}) \times 2.5$$

where

a = 1 to A, A = total number of administrations

Confidential Page 17 of 35

 S_{L_a} = number of sprays to the left nostril during administration a S_{R_a} = number of sprays to the right nostril during administration a

Total exposure E_T (mg) will be calculated as

$$E_T(mg) = \sum_{a=1}^{A} E_a (mg)$$

Duration of Exposure E_D (days) is defined as the total number of days that treatment was administered, ie,

$$E_D$$
 = date of last dose – date of first dose + 1

Mean daily exposure E_M (mg) will be calculated for each subject as

$$E_M (mg) = \frac{E_{T (mg)}}{E_{D (days)}}$$

and will be rounded to the nearest hundredth.

Listings and summaries will be based on the Safety Population. Listings will show each study treatment administration per nostril and will also display cumulative total exposure, duration of exposure, and mean daily exposure.

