### 6.1 Study Treatment(s) Administered

#### 6.1.1 The Drug-device Study Treatment

The study treatment (OP0201 and the placebo) is manufactured using Good Manufacturing Processes (GMP) with development phase appropriate compliance with global Health Authority guidelines by [REDACTED]. It is considered a drug-device combination product because the drug is expelled from a pressurized canister via an actuating device.

The study treatment is supplied in mechanical packing parts that includes a pressurized canister with a securely attached metering valve where the OP0201 or placebo is contained, an actuator device into which the canister is seated, and an angled tip on the device to deliver the drug to the nostrils. The pressurized canisters are labeled to deliver 100 actuations (sprays) per canister.

Parents/caregivers will be given a demonstration of the administration of the study treatment and will need to be trained on study treatment administration on Day 1, prior to the first dose (which will be given under supervision of the study center staff).

All Medical Device Incidents, including those resulting from malfunctions of the device, must be detected, documented, and reported by the Investigator throughout the study (see Section 8.4.6).

Participants' parents/caregivers will be trained on the proper administration of the study treatment and antibiotics on Day 1, prior to the first dose. The first dose will be administered under the supervision of the study staff by the parent/caregiver.

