#### 6.1.2 OP0201

OP0201 is the active drug. It is a drug-device combination product comprised of DPPC:CP (approximately 20:1 w/w in HFA 134a) for intranasal administration.

Each spray of OP0201 delivers 2.5 mg of active ingredients. Participants randomized to OP0201 will receive 2 sprays per nostril BID (morning and evening, at a total daily dose of 20 mg) for a total of 20 doses.

See the IB for further details regarding OP0201.

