### **6.1.3 Placebo**

Placebo is the propellant without any active ingredients (HFA 134a only) and provides a total daily dose of 0 mg.

All Participants will receive the same intranasal dosing regimen of placebo (given as 2 sprays to each nostril BID) for a total of 20 doses.

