7. ANALYSIS POPULATIONS

Screened Population: Subjects whose parent/legal guardian signed the informed consent form.

Confidential Page 12 of 35

Safety Population: Subjects who received at least one intranasal spray of study treatment. Subjects will be summarized and analyzed based on treatment received.

Modified Intent to treat (mITT) Population: Subjects who were randomized excluding the first 3 subjects dosed (subject numbers 1001, 1002 and 1003), as there was a known device malfunction for these subjects. Subjects will be summarized and analyzed based on randomization assignment, regardless of treatment received.

Per Protocol (PP) Population: Subset of the mITT population with no protocol violations that may have affected the primary efficacy endpoint family.

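### SAP 10.1 converts sprays to mg at 2.5 mg each with no term for treatment group, so placebo children would be reported with the OP0201 exposure instead of 0 mg

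*SAP*

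**What the plan says.** SAP 10.1 introduces its rule with "Exposure per study treatment administration E_a (mg) will be calculated as" and gives a single expression, the number of sprays to the left nostril plus the number to the right, multiplied by 2.5. Total exposure E_T is the sum of E_a over administrations. Mean daily exposure E_M is E_T divided by the duration of exposure E_D, which is the last dose date minus the first dose date, plus 1. No term, footnote or exception refers to treatment group.

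On who is included, SAP 10.1 says: "Listings and summaries will be based on the Safety Population". SAP 7 defines that population as "Subjects who received at least one intranasal spray of study treatment", analysed by treatment received. Protocol 6.1.1 counts placebo as study treatment, so both arms are in. SAP Appendix B lists Table 14.1.9.1 and Listing 16.2.5.1 on the same population.

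On content per spray, Protocol 6.1.2 states: "Each spray of OP0201 delivers 2.5 mg of active ingredients". Protocol 6.1.3 states: "Placebo is the propellant without any active ingredients (HFA 134a only) and provides a total daily dose of 0 mg". The synopsis, under Treatment Groups and Duration, also gives placebo as 0 mg. SAP 16, which lists the departures from the protocol, has no entry on exposure.

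**The concern.** The 2.5 factor is a property of the OP0201 spray, but the SAP applies it to any spray of study treatment. A program written to the SAP would therefore give a mg value to children who receive propellant only, and the exposure table would show no mg contrast between the arms.

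Safety and tolerability are among the primary objectives, and the protocol reports that only 1 child had previously received the active ingredients intranasally. The exposure table gives the dose context in which the safety data are read, so its placebo column should agree with the protocol.

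**Working it through.** **Inputs**
- mg per spray in the SAP formula: 2.5 (SAP 10.1), with no arm term.
- OP0201 regimen: "2 sprays per nostril BID (morning and evening, at a total daily dose of 20 mg) for a total of 20 doses" (Protocol 6.1.2).
- Placebo regimen: the same number of sprays, nostrils, daily administrations and doses (Protocol 6.1.3).
- Placebo content: 0 mg (Protocol 6.1.3 and synopsis).

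**Step 1: reproduce the protocol's OP0201 figure.**
- E_a = (2 + 2) x 2.5 = 10 mg per administration.
- Two administrations a day: 2 x 10 = 20 mg/day.
- 20 administrations: E_T = 20 x 10 = 200 mg.

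The 10 mg and 20 mg/day match the protocol exactly. The formula is correct for OP0201.

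**Step 2: apply the same formula to a fully adherent placebo child.**
- Sprays: 20 x 4 = 80.
- E_a = 4 x 2.5 = 10 mg.
- E_T = 80 x 2.5 = 200 mg.
- E_M = 200 / 10 = 20.00 mg/day if E_D is 10 days.
- E_M = 200 / 11 = 18.18 mg/day if the 20 doses span 11 calendar days, for example one dose on the first day, two on each of the next nine and one on the last (1 + 18 + 1 = 20).

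The protocol value is 0 mg for all of these.

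**Step 3: allow for incomplete adherence (assumed levels).**
- 90% of sprays taken: 72 x 2.5 = 180 mg.
- 80% of sprays taken: 64 x 2.5 = 160 mg.

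The placebo value falls with adherence, but it is 0 only for a child with no recorded sprays, who would not be in the Safety Population.

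**Step 4: set the factor by arm.**

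| Fully adherent, 10 days | E_a | E_T | E_M |
|---|---|---|---|
| OP0201, 2.5 mg per spray | 10 mg | 200 mg | 20.00 mg/day |
| Placebo, 0 mg per spray | 0 mg | 0 mg | 0.00 mg/day |

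**Step 5: trace where the factor goes.** It enters E_a, E_T and E_M only. E_D is a difference of dates. Compliance in SAP 10.2.1 divides spray counts by expected sprays (8 a day) and uses E_D, but not the 2.5. The safety endpoints in SAP 4.2.1 are adverse events and shifts in examinations and vital signs. The efficacy models and the power calculation make no use of exposure.

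**The case against.** The strongest reply is that this is a missing qualifier and that no competent programmer would report mg of active drug in a column headed Placebo. SAP 10.1 speaks of study treatment exposure, not of exposure to the active ingredients, and the table columns are labelled by arm. The mock-up tables are separate documents approved together with the SAP (SAP 8.2), and they may already deal with placebo.

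Part of this stands. The mock-ups cannot be checked, so what the final table will show is not certain, and a reader who sees the column label is unlikely to be misled about what placebo contains. But the SAP is the specification, its stated unit is mg, and nowhere does it describe the figure as nominal or spray-equivalent. Followed literally, it gives a value that the protocol contradicts.

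Three stronger readings are tempting, and the documents do not support them.
- A reader might infer that paediatric exposure would be overstated about twofold. That needs the arms to be pooled. SAP 8.2 says only that some tables may carry an all-subjects column, and nothing says that the exposure table will.
- A reader might multiply up to 70 x 200 = 14,000 mg of exposure that did not occur. E_T and E_M are per-child quantities, no planned output sums mg over an arm, and the figure assumes full adherence in every placebo child.
- A reader might add that subjects 1001 to 1003 would be credited with full doses from a faulty device. SAP 7 says only that they leave the mITT population "as there was a known device malfunction for these subjects". The documents do not say how the fault affected delivery, how many sprays it affected, or which arm these children were in, so no dose error can be derived.

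**Conclusion.** The point holds and is of low severity. As written, SAP 10.1 gives a fully adherent placebo child 200 mg in total and 20 mg/day (18.18 mg/day over 11 calendar days), where the protocol gives 0. At assumed adherence of 80% to 90% the total is 160 to 180 mg.

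This rests on reading the formula as applying to both arms. The SAP does not say so in words, but it follows from the absence of an arm term, the use of the Safety Population and the inclusion of placebo in study treatment. That the two arms would look alike also assumes similar numbers of sprays taken, which the identical regimen makes reasonable. The damage is limited to E_a, E_T and E_M in one table and one listing, and no test or conclusion of the trial depends on them.

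**What to change.** In SAP 10.1, replace the constant 2.5 with a factor set by treatment actually received: 2.5 mg per spray for OP0201 and 0 mg per spray for placebo. Summarise number of sprays, number of doses and duration of exposure for both arms in Table 14.1.9.1, so that the arms can be compared on a quantity that means the same thing in each. Check the mock-ups for Table 14.1.9.1 and Listing 16.2.5.1 against the revised text.

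The cost is a sentence in the SAP and about one line of programming. Spray counts per nostril and administration are already planned for the listing, so no new data are needed.

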10.2 Study Treatment and Oral Antibiotic Compliance

10.2.1 Study Treatment Compliance

Study treatment compliance will be expressed as both overall and mean daily percent compliance. For mean daily percent compliance, only days on which exposure occurred will be counted.

Percent compliance will be calculated for each study day of exposure as

$$C_d = 100 x \left(S_{L_{ACTUAL_d}} + S_{R_{ACTUAL_d}} \right) / 8$$

rounded to the nearest tenth, where

d = 1 to D, D = total number of study days of exposure $S_{L_ACTUAL_d} = actual$ number of sprays to the left nostril on day d $S_{R_ACTUAL_d} = actual$ number of sprays to the right nostril on day d

For subjects who prematurely discontinue treatment, percent compliance will be calculated only for study days prior to discontinuation.

Confidential Page 18 of 35

Percent overall compliance C_T will be calculated as

$$C_T = 100 X \frac{\sum_{d=1}^{D} \left(S_{L_{ACTUAL_d}} + S_{R_{ACTUAL_d}} \right)}{S_{EXPECTED}}$$

rounded to the nearest tenth, where

$$S_{EXPECTED} = E_D x 8$$

with E_D as defined in Section 10.1.

Mean daily percent compliance C_M will be calculated for each subject as

$$C_M = \frac{\sum_{d=1}^D C_d}{E_D}$$

and will be rounded to the nearest hundredth.

Listings and summaries will be based on the Safety Population. Listings will show compliance for each study day and will also display cumulative overall compliance and mean daily compliance.

10.2.2 Oral Antibiotic Compliance

Oral antibiotic exposure will be collected by diary as number of administrations. Daily and overall antibiotic compliance will be calculated as 100 x (number of administrations / expected number of administrations) rounded to the nearest tenth. For daily compliance, the expected number is 2. For overall compliance, the expected number is the number of days of study participation x 2; ie, for subjects who prematurely discontinue from the study, compliance will be calculated only for study days prior to discontinuation. Oral antibiotic compliance will be listed and summarized for the Safety Population.

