## 4.0 STUDY DESIGN

### 4.1 Overall Design

This is a Phase 2a, single center, double-blind, randomized, placebo-controlled, parallel group study to assess the safety, tolerability, and efficacy of 20 mg per day intranasal OP0201 (10 mg administered BID for a total of 20 doses) as an adjunct therapy to oral antibiotic treatment of AOM in infants and children aged 6 to 24 months (inclusive). Participants will be followed for up to 20 days after study treatment is discontinued. The total duration of study participation for each Participant is up to 30 days, which includes 4 clinic visits: Visit 1: (Day 1) Screening/Enrollment and initiation of the study treatment and oral antibiotics administration; Visit 2: (Day 4 [+2]); Visit 3: (Day 12 [+2]); and Visit 4: (Day 28 [ $\pm 2$ ]) Study Exit. On Day 1 potential Participants' parents/legal guardians in attendance at the study center will be told about the study and those Participants whose parents/legal guardian provide written informed consent will be evaluated for study eligibility. Those who meet all inclusion and no exclusion criteria will be enrolled and randomized (1:1 ratio) to receive a total of 20 intranasal doses (over approximately 10 days) with 20 mg per day OP0201 (10 mg BID) or placebo as an adjunct treatment to standard oral antibiotics (amoxicillin-clavulanate given BID for 20 doses).

Parents/caregivers of the Participants will complete an electronic daily diary on all days when study treatment is given (approximately 10 days) to record BID administration of the oral antibiotic and study treatment, and to record daily AOM-SOS scores.

At each study visit, assessments include a physical examination (including visual examination of the nasopharynx and oropharynx) and measurement of vital signs, pneumatic otoscopy to assess TM of each ear, endoscopic examination with image capture of each ear when possible, and tympanogram (to be performed when possible) of each ear. Adverse events and concomitant medication use will be recorded. At the Day 12 Visit, parents/caregivers will complete the Device Experience Questionnaire. The study assessments are summarized in [Table 3](#).

An unscheduled interim/sick visit may occur for safety purposes or if AOM symptoms have relapsed or worsen. Applicable procedures (eg, physical, otoscopy, tympanometry) will be performed and recorded in the electronic case report form (eCRF).

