### **6.1.4 Standard Antibiotic**

Participants will be prescribed a standard 10-day (20 doses) oral antibiotic treatment course of amoxicillin-clavulanate at a total dose of 90 mg/6.4 mg/kg/day administered orally in 2 divided doses (12-hourly).

Children categorized as initial antibiotic treatment failure (no clinical improvement within 48 to 72 hours) will receive appropriate antibiotic therapy which may include intramuscular ceftriaxone 75 mg/kg at the time of treatment failure, and a repeat dose in 48 hours.

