3. STUDY DESIGN

This is a Phase 2a, single-center, double-blind, randomized, placebo-controlled, parallel-group study to assess the safety, tolerability, and efficacy of 20 mg per day intranasal OP0201 (10 mg administered twice/day (BID) over 10 days for a total of 20 doses) as an adjunct therapy to oral antibiotic treatment of AOM in infants and children aged 6 to 24 months (inclusive). Subjects will be followed for up to 20 days after study treatment is discontinued. The total duration of study participation for each subject is up to 30 days, which includes 4 clinic visits. An unscheduled interim/sick visit may occur for safety purposes or if AOM symptoms have relapsed or worsened. The Schedule of Activities is in Appendix A.

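### Overall antibiotic compliance is divided by all study days, so a fully adherent completer scores 33.3% to 38.5%, and the study-drug compliance formulas conflict with their own definitions

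*SAP*

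**What the plan says.** **Antibiotic.** Protocol 6.1.4 prescribes a "standard 10-day (20 doses) oral antibiotic treatment course". SAP 10.2.2 states: "Oral antibiotic exposure will be collected by diary as number of administrations". Under Protocol 4.1 that diary is kept on study-treatment days, about 10 in all. Daily compliance uses an expected number of 2. For the overall figure: "For overall compliance, the expected number is the number of days of study participation x 2". The only shortening is for children who leave the study early. SAP 3 uses the same term elsewhere: "The total duration of study participation for each subject is up to 30 days". Protocol 6.1.4 also provides for a change of antibiotic: "Children categorized as initial antibiotic treatment failure (no clinical improvement within 48 to 72 hours) will receive appropriate antibiotic therapy". SAP 10.2.2 does not say how those administrations are counted.

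**Study drug.** SAP 10.1 describes duration of exposure, E_D, in words as "defined as the total number of days that treatment was administered", and then gives the formula "date of last dose – date of first dose + 1". SAP 10.2.1 says that mean daily compliance counts only days with exposure and defines D as the number of those days, but its formula divides by E_D. Overall compliance uses E_D x 8 sprays as the expected number. The daily denominator is fixed at 8 sprays.

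SAP 16, which lists changes from the protocol, does not mention compliance.

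**The concern.** In the antibiotic measure, the numerator stops growing when the course ends, at about 20 administrations, while the denominator keeps growing until study exit. The overall percentage then mostly reflects how long the child stayed in the study. It also contradicts the daily measure in the same section: a child at 100% on each of 10 days would be about one-third compliant overall.

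For study drug, two programmers could follow the same section and obtain different values for duration, mean daily exposure and mean daily compliance, depending on whether they followed the words or the formula.

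At stake are Tables 14.1.9.1, 14.1.9.2.1 and 14.1.9.2.2 and their listings. OP0201 is tested as an adjunct to the antibiotic, so readers will use these outputs to judge whether background therapy and study drug were taken as planned in both arms.

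**Working it through.** The plan states no compliance percentage to reproduce. Its regimen figures do check: 10 days x 2 = 20 antibiotic doses; 2 sprays x 2 nostrils x 2 times daily = 8 sprays a day; 8 x 2.5 mg = 20 mg a day; 10 x 8 = 80 sprays.

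**Inputs**
- Course of 20 doses: Protocol 6.1.4.
- Exit window Day 26 to Day 30: SAP 8.7.
- Antibiotic formula, 100 x administrations / expected administrations: SAP 10.2.2.
- E_D, D, daily compliance C_d, overall compliance C_T, mean daily compliance C_M and mean daily exposure E_M: SAP 10.1 and 10.2.1.

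**Antibiotic, as written:** 100 x doses / (2 x days of participation).

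| Child | Calculation | Overall compliance |
|---|---|---|
| 20 doses, exit Day 26 | 20/52 | 38.5% |
| 20 doses, exit Day 28 | 20/56 | 35.7% |
| 20 doses, exit Day 30 | 20/60 | 33.3% |
| 20 doses, leaves with 14 days counted | 20/28 | 71.4% |
| 20 doses, leaves with 13 days counted | 20/26 | 76.9% |
| 11 doses, leaves with 14 days counted | 11/28 | 39.3% |
| 10 doses by Day 5, stays to Day 28 | 10/56 | 17.9% |
| 10 doses by Day 5, leaves with 5 days counted | 10/10 | 100% |

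The ranking can reverse: 11 of 20 doses with early exit (39.3%) scores above all 20 doses with exit at Day 28 (35.7%). The last two children took the same number of doses and differ only in time on study.

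**Study drug: C_M and C_T are the same quantity.** With S_d the sprays on day d, C_d = 100 x S_d / 8. Then C_M = sum(C_d) / E_D = 100 x sum(S_d) / (8 x E_D) = C_T, apart from rounding. This is true whichever meaning E_D takes.

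**One full day missed between first and last dose, otherwise full dosing over 10 dates.** Sprays = 72, D = 9, span = 10.
- E_D by the formula: C_T = C_M = 72/80 = 90.0%. The exposure-days rule gives 900/9 = 100%. E_M = 180/10 = 18.00 mg.
- E_D by the words: C_T = C_M = 72/72 = 100%, so the overall measure misses the skipped day. E_M = 180/9 = 20.00 mg.

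**Last day missed.** Span = D = 9, so C_T = C_M = 72/72 = 100% under either meaning, although 8 of 80 scheduled sprays were not taken (72/80 = 90.0%).

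**All 80 sprays over 11 dates.** Assume an evening first dose: 4 sprays, nine days of 8, then 4. Span = D = 11, so C_T = 80/88 = 90.9%. The mean of C_d is (50 + 900 + 50)/11 = 90.9%, so dividing by D alone does not repair this case.

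With full dosing over exactly 10 dates, every study-drug version gives 100%.

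**The case against.** - **The authors may have meant the diary period.** The section opens with diary collection, and the clause on early leavers suggests that the aim was only to shorten the denominator for them. That may well be the intent, but no text says so. The clause is tied to leaving the study, whereas SAP 10.2.1 shortens at treatment discontinuation. The 33.3% to 38.5% range is therefore what the rule gives as written; it is not proof of what would be programmed.
- **The general convention settles E_D.** SAP 8.6 defines duration as end date minus start date plus 1, which favours the formula. This has force for E_D itself. It makes the C_M problem definite, because C_M then divides by a calendar span although the text says that only exposure days count.
- **Some points are matters of design.** Two measures that coincide are redundant, not wrong in themselves. Ending the denominator at the last dose is the stated rule for children who stop treatment early. The missed-last-day problem therefore applies to children who did not discontinue treatment.
- **The examples are chosen.** The ranking reversal needs a particular early leaver, and the 11-date case assumes a single dose on Day 1. Both are illustrations. The 33.3% to 38.5% result needs no such case: it applies to every fully adherent completer within the exit window.
- **The output is descriptive.** This is correct. The administrations, daily compliance and diary entries are also listed, so the data can be recovered.
- **A fixed denominator has its own gap.** Protocol 6.4 says that dosing resumes at the next scheduled time after a miss, without saying whether missed doses are added at the end. If they are, 20/20 or 80/80 could describe a child who skipped a day and finished late. This stands, and the SAP wording should cover it.

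**Conclusion.** The concern holds. Following SAP 10.2.2 as written, a completer who takes all 20 doses is reported at 33.3% to 38.5% overall antibiotic compliance, against 100% of the planned course. This rests on reading study participation as SAP 3 uses it; no text limits it to the course or the diary period.

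The study-drug definitions conflict on the page. The word and formula versions of E_D give different results only when a whole day between first and last dose is missed: for one such day, C_M is 90.0% by the formula against 100% by the stated rule, and E_M is 18.00 mg against 20.00 mg. The missed-last-day and 11-date distortions are separate and occur under either meaning of E_D.

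The effect is confined to descriptive exposure and compliance outputs. No efficacy test, compliance threshold or stated per-protocol rule depends on them, and daily antibiotic compliance on full dosing days is unaffected. The SAP should still be corrected, because the tables would mislead as specified.

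**What to change.** **Antibiotic (SAP 10.2.2).** Set the expected number to the doses of the planned course scheduled up to the earlier of course completion or discontinuation. Cap it at 20 and count doses rather than days x 2, so that a course spread over 11 dates still has 20 expected. State how administrations are counted for children switched to another antibiotic under Protocol 6.1.4.

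**Study drug (SAP 10.1 and 10.2.1).**
- Reconcile the words and formula for E_D, and say which meaning E_M uses.
- Divide C_M by D, and use the sprays scheduled on that day in C_d.
- Base the expected number in C_T on scheduled doses: 80 sprays for children who do not discontinue study treatment early, otherwise the sprays scheduled before treatment discontinuation.

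With these changes, one interior day missed gives C_T = 72/80 = 90.0% and C_M = 900/9 = 100%, so the two measures carry different information. A missed last day gives C_T = 90.0%, and 80 sprays over 11 dates gives 100% on both.

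For both products, state how any doses taken after the planned end to replace missed ones are counted.

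The cost is SAP wording in three subsections and a few lines of code. No new data are needed.
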